#### **4.4.1.2. Main Analytical Approach**

All participant files from Fitabase will be downloaded and coded according to the current version of the Fitabase Garmin Data Dictionary (Last updated version 6/4/2020 as of time of writing). Only data from those participants who meet criteria for the Full Analysis set will be analyzed. Data for this exploratory endpoint will be statistically analyzed via a repeated measures ANOVA, comparing baseline changes in activity and sleep to each of the treatment month(s) activity and sleep. Significant changes will be followed up using within groups, repeated measures *t*-tests as needed.

#### **4.4.2. Change in Functional Assessment of Migraine Scale (FAMS) Total Scores from Baseline to Each 4-Week Treatment Period**

##### **4.4.2.1. Definition of Endpoint**

Two versions of the Functional Assessment of Migraine Scale (FAMS) were administered to participants, including Research (FAMS-R) and Research Supplement (FAMS-RS). FAMS total score consists of all 27-items from both FAMS-R and FAMS-RS, self-administered in the form of a questionnaire, which evaluates the complete patient with migraine and their response to treatment. The FAMS total score is derived from the summation of all 27 questions. The range of total FAMS score is 27 to 135 (with lower scores indicating greater daily life burdens due to migraine).

##### **4.4.2.2. Main Analytical Approach**

See Appendix 6.3.7 for FAMS scoring information. Only data from those participants who meet criteria for the Full Analysis set will be analyzed. Data for this exploratory endpoint will be analyzed via a repeated measures ANOVA, comparing mean changes in participant's Functional Assessment of Migraine Scale (FAMS) total scores from baseline (Visit 2) to each of the 4-week treatment periods (Visit 3, 4, and 5). Significant changes will be followed up using within groups, repeated measures *t*-tests as needed.

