### 6.3.7. Functional Assessment of Migraine Scale (FAMS)

#### Functional Assessment of Migraine Scale – Research (FAMS-R)™

The purpose of this survey is to identify questions that would help assess your migraine treatment and improvement with your provider or for research purposes.

For each item mark (circle) your agreement with the statement from strongly disagree to strongly agree based on the last month of your migraine treatment and symptoms.

1. My migraine associated symptoms are negatively impacting my life.  

5 Strongly Disagree	4 Somewhat Disagree	3 Neither Agree nor Disagree	2 Somewhat Agree	1 Strongly Agree
------------------------	------------------------	---------------------------------	---------------------	---------------------
2. The number of my head pain days have decreased.  

1 Strongly Disagree	2 Somewhat Disagree	3 Neither Agree nor Disagree	4 Somewhat Agree	5 Strongly Agree
------------------------	------------------------	---------------------------------	---------------------	---------------------
3. My migraine associated symptoms prevent me from doing my normal activities.  

5 Strongly Disagree	4 Somewhat Disagree	3 Neither Agree nor Disagree	2 Somewhat Agree	1 Strongly Agree
------------------------	------------------------	---------------------------------	---------------------	---------------------
4. My migraines prevent me from scheduling activities.  

5 Strongly Disagree	4 Somewhat Disagree	3 Neither Agree nor Disagree	2 Somewhat Agree	1 Strongly Agree
------------------------	------------------------	---------------------------------	---------------------	---------------------
5. I now have fewer migraine attacks.  

1 Strongly Disagree	2 Somewhat Disagree	3 Neither Agree nor Disagree	4 Somewhat Agree	5 Strongly Agree
------------------------	------------------------	---------------------------------	---------------------	---------------------
6. My migraines make me miss too much work.  

5 Strongly Disagree	4 Somewhat Disagree	3 Neither Agree nor Disagree	2 Somewhat Agree	1 Strongly Agree
------------------------	------------------------	---------------------------------	---------------------	---------------------
7. My migraine attacks decrease my feelings of self-worth.  

5 Strongly Disagree	4 Somewhat Disagree	3 Neither Agree nor Disagree	2 Somewhat Agree	1 Strongly Agree
------------------------	------------------------	---------------------------------	---------------------	---------------------

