8. My number of severe head pain days has decreased.  

1 Strongly Disagree	2 Somewhat Disagree	3 Neither Agree nor Disagree	4 Somewhat Agree	5 Strongly Agree
------------------------	------------------------	---------------------------------	---------------------	---------------------
9. My migraines negatively affect my relationships.  

5 Strongly Disagree	4 Somewhat Disagree	3 Neither Agree nor Disagree	2 Somewhat Agree	1 Strongly Agree
------------------------	------------------------	---------------------------------	---------------------	---------------------

© Copyright Clinvest Research LLC 2019

This document, including any source code, is the property of [Clinvest Research LLC](#), and may contain proprietary, confidential, or legally privileged information. No part of this report, or any information contained therein, may be disseminated without the written consent of [Clinvest Research LLC](#).

**Functional Assessment of Migraine Scale – Research  
(FAMS-R)™**

10. I know that my migraine medication will relieve my migraine symptoms.

1 Strongly Disagree	2 Somewhat Disagree	3 Neither Agree nor Disagree	4 Somewhat Agree	5 Strongly Agree
------------------------	------------------------	---------------------------------	---------------------	---------------------

11. My migraines limit my social activities.

5 Strongly Disagree	4 Somewhat Disagree	3 Neither Agree nor Disagree	2 Somewhat Agree	1 Strongly Agree
------------------------	------------------------	---------------------------------	---------------------	---------------------

12. Overall, my head pain has decreased.

1 Strongly Disagree	2 Somewhat Disagree	3 Neither Agree nor Disagree	4 Somewhat Agree	5 Strongly Agree
------------------------	------------------------	---------------------------------	---------------------	---------------------

13. I am not improving because the brain fog that occurs with migraine makes it difficult for me to continue about my day.

5 Strongly Disagree	4 Somewhat Disagree	3 Neither Agree nor Disagree	2 Somewhat Agree	1 Strongly Agree
------------------------	------------------------	---------------------------------	---------------------	---------------------

14. I have been able to complete more daily tasks because I have less head pain.

1 Strongly Disagree	2 Somewhat Disagree	3 Neither Agree nor Disagree	4 Somewhat Agree	5 Strongly Agree

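### FAMS change from baseline is taken on a sum that includes five ratings of change, whose Visit 2 answers are not a functional baseline

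*SAP*

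**What the plan says.** SAP 4.4.2.1 defines the analysed score: "The FAMS total score is derived from the summation of all 27 questions", that is, 18 FAMS-R items plus 9 FAMS-RS items, with a range of 27 to 135 and lower values meaning greater burden. SAP 4.4.2.2 then plans a repeated measures ANOVA, which it describes as "comparing mean changes in participant's Functional Assessment of Migraine Scale (FAMS) total scores from baseline (Visit 2) to each of the 4-week treatment periods".

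The form in SAP Appendix 6.3.7 asks for FAMS-R answers "based on the last month of your migraine treatment and symptoms". Most of its items describe present burden. Five do not:

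- Item 2: "The number of my head pain days have decreased"
- Item 5: "I now have fewer migraine attacks"
- Item 8: "My number of severe head pain days has decreased"
- Item 12: "Overall, my head pain has decreased"
- Item 14: "I have been able to complete more daily tasks because I have less head pain"

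All five score 5 for the strongest agreement, and none names the time it is compared with. Item 13 is a partial sixth, because it combines not improving with a current difficulty. SAP 4.4.3.1 excludes only items 10 and 17 from the Functioning Subscale, so the five items are in that score as well as in the FAMS-R Total. Neither document gives a rule for these items at Visit 2 or analyses them separately.

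**The concern.** A change score needs the same quantity measured before and after. A burden item meets that need. A rating of change does not: its answer before treatment says whether things were already getting better, not how well the participant functions.

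The design makes this matter. Visit 2 questionnaires come before the first injection (Protocol 4.1). Participants must have had stable migraine for at least three months (Protocol 5.1, criterion 9), recent changes in preventive medication are excluded (Protocol 5.2, criterion 13), and usual treatment continues through the run-in. Most participants therefore have little reason to agree at Visit 2 that headaches have lessened, whether their burden is mild or severe. Subtracting that answer from a later rating of change gives a change of a change. With one arm (Protocol 6.3), no control group shares the effect and cancels it.

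At stake is the exploratory objective on functional impact. Part of the FAMS change could reflect the fact that treatment has started rather than better function, and the pattern across months could depend on how participants read the items. The correlations in SAP 4.4.3 are also touched, because they set a score mixing change and status against measures that are largely of status.

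**Working it through.** **Inputs from the SAP.** Each item is scored 1 to 5. There are 27 items in the analysed total, 18 in FAMS-R and 16 in the Functioning Subscale.

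**The plan's own range.** 27 × 1 = 27 and 27 × 5 = 135, which agrees with SAP 4.4.2.1.

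**Share carried by the five items.** Their span is 5 × (5 − 1) = 20 points.

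| Score | Span | Share | Where used |
|---|---|---|---|
| 27-item total | 27 × 4 = 108 | 20/108 = 18.5% | Change analysis (4.4.2) and correlations (4.4.3) |
| FAMS-R Total | 18 × 4 = 72 | 20/72 = 27.8% | Correlations only |
| Functioning Subscale | 16 × 4 = 64 | 20/64 = 31.3% | Correlations only |

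**Gain from the five items alone.** Let *b* be the Visit 2 answer and *f* the later answer, equal on all five items. The contribution is 5 × (*f* − *b*). The documents give no item data, so *b* = 1 to 3 is an assumption.

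- *f* = 5: 5 × (5 − 3) = 10, 5 × (5 − 2) = 15, 5 × (5 − 1) = 20.
- *f* = 4: 5, 10 and 15 for the same baselines.

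**Course over time when a benefit is held.** Assume the other 11 Functioning items (16 − 5) each improve by 1 point by Visit 3 and stay there, and that items 10 and 17 and the nine FAMS-RS items do not move. Assume the five items are at 3 at Visit 2 and 5 at Visit 3. What follows depends on how they are read:

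| Reading of the five items | Answer at Visits 4-5 | 27-item change at Visits 3, 4, 5 | Change without the five items |
|---|---|---|---|
| Since treatment began | 5 | +21, +21, +21 | +11, +11, +11 |
| Within the last month | 3 | +21, +11, +11 | +11, +11, +11 |

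In the second row the total drops by 10 of 21 points (48%) with no clinical change. If the later answers are 2 or 1 instead of 3, the fall from Visit 3 is 15 or 20 points. The score without the five items is the same under both readings.

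**Ranges after removal.** The total becomes 22 items, 22-110, and Functioning becomes 11 items, 11-55. With item 13 also removed, the total becomes 21 items, 21-105, and Functioning becomes 10 items, 10-50.

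**The case against.** The best defence is that FAMS is used as intended. SAP 4.4.2.1 says that it evaluates response to treatment as well as the patient, so response items are deliberate content. This explains why the items are on the form. It does not make their pre-treatment answers a baseline. Nor does following the form settle the matter: the two forms define an 18-item total and several subscales, but no 27-item total. That sum is the SAP's own.

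Other objections stand and limit the point:

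- **Baseline is not forced low.** A stable participant may choose the neutral answer, 3. One on a stable preventive, allowed by Protocol 5.1 criterion 10, may agree that attacks are fewer since starting it. At or below the midpoint is an expectation, not a certainty.
- **The fall after Visit 3 needs one reading.** The instruction sets a recall window and does not ask for comparison with the previous month. Item 5 reads naturally as fewer than before treatment, and a held benefit then keeps its score.
- **Burden items would move too.** Real improvement should also show in items such as 3, 4, 11 and 16, which keep a held benefit visible.

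A reader might go further and infer that a sustained benefit would appear as a loss against baseline. The documents do not support that. The five items contribute negatively only if later answers are below those at Visit 2. Under the literal reading, a held benefit and a stable run-in are both months without further decrease, so the answers should be similar and the contribution near zero. What can occur is attenuation from Visit 3.

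**Conclusion.** The point holds as a limited flaw in an exploratory analysis. The planned FAMS change mixes status items with five ratings of change whose Visit 2 answers do not measure function. They hold 18.5% of the range of the score analysed for change. The larger shares, 27.8% and 31.3%, belong to scores used only in the correlations and should not be applied to the change analysis.

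The 10 to 20 point gain assumes baseline answers of 1 to 3 and later answers of 5. Apparent shrinkage from Visit 3 to Visits 4-5 additionally assumes a literal last-month reading, which the form permits but does not force. The gain from the missing functional baseline does not depend on that reading.

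Functional impact is carried mainly by the MFIQ as primary and secondary endpoints. Neither those results nor N = 54 is affected.

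**What to change.** Keep the planned 27-item analysis and make these additions to the SAP:

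1. In 4.4.2, add a change-from-baseline analysis on the FAMS score without items 2, 5, 8, 12 and 14, both for the total (22 items, 22-110) and for the Functioning Subscale (11 items, 11-55). Repeat it with item 13 also removed as a check. Base the interpretation of functional impact on the reduced score.
2. Report the five items as direct ratings at Visits 3, 4 and 5, without subtracting Visit 2, and note that the form states no reference point.
3. In 4.4.3, add the reduced Functioning score to the correlations.

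The cost is a few sentences and simple derived scores, with no new data. The downside is that the reduced score is not a published subscale, so the planned totals should stay in the report for comparison. SAP 4.4.2.1 refers to FAMS administration in the past tense, so collection had at least begun. Adding a score rather than replacing the endpoint avoids redefining it at that stage. The addition should be dated in the SAP version history, and labelled post hoc if it is made after database lock.

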#### **4.4.3. Correlation Between Functional Impact of Migraine Scale (FAMS) Total and Domain Subscale Scores and Other Migraine Related Patient Reported Outcome (PRO) Measures**

##### **4.4.3.1. Definition of Endpoint**

See section 4.4.2.1 for full definition of FAMS total score. The FAMS-R consists of 18 items. Scores can be derived as the Total Score from the summation of all 18 items (range 18-90) or as the Functioning Subscale Score from the summation of all items except 10 and 17 (range 16-80). Both the Total and Functioning Subscale Scores interpret lower scores as an indication of greater daily life burdens due to migraine. Additionally, the FAMS-R includes a Medicine Subscale Score from the summation of only items 10 and 17 (range 2-10), which interprets lower scores as an indication of lower confidence in the efficacy of migraine medication.

The FAMS-RS consists of 9 items. Scoring is divided across three subscales: Finance/Insurance Score (summation of items 1-3), Doctor/Provider Score (summation of items 4-6), and Education Score (summation of items 7-9), all of which range from 3-15. All subscales interpret lower scores as a greater day-to-day burden across the related subscale items. The PRO measures include Global MFIQ (see section 4.2.1), MIBS-4 (see section 4.3.3.1), WPAI-M (see section 4.3.5.1), SDSF (see section 4.3.6.1), GSE-SF (see section 4.3.7.1), and BMWS (see section 4.3.8.1) scores.

##### **4.4.3.2. Main Analytical Approach**

Only data from those participants who meet criteria for the Full Analysis set will be analyzed. Data for this exploratory endpoint will be analyzed via bivariate correlations between FAMS (total and subscales) and each of the above listed PRO measures. See Appendix 6.3 for scoring information on each of the measures.

#### **4.5. Safety Analyses**

The protocol states safety analyses would evaluate the safety and tolerability of participants treated with erenumab-aooe via collection of adverse events and safety evaluations. However, there will not be a formal statistical analysis for safety endpoints; rather, all safety endpoints will be summarized via tables and descriptive statistics as appropriate. Planned time points for all safety assessments are provided in the SoA.

##### **4.5.1. Adverse Events (AEs)**

Medical Dictionary for Regulatory Activities (MedDRA) Version 24.1 will be used to code all adverse events. AEs will be reported by the participant (or, when appropriate, by a caregiver, surrogate, or the participant's legally authorized representative), or identified by research staff during study safety assessment procedures. These AE descriptions will be updated in the final report via mapping to the MedDRA Naming Hierarchy, using verbatim terms (e.g., feeling

This document, including any source code, is the property of [Clinvest Research LLC](#), and may contain proprietary, confidential, or legally privileged information. No part of this report, or any information contained therein, may be disseminated without the written consent of [Clinvest Research LLC](#).

queasy) mapped to MedDRA Preferred Terms (PT) (e.g., Nausea), Highest Level Term (HLT), Highest Level Group Term (HLGT) and System Organ Class (SOC). Final AE tables will be created using the most appropriate MedDRA hierarchy for each AE class.

The investigator and any qualified designees are responsible for detecting, documenting, and recording events that meet the definition of an AE or serious adverse event (SAE) and remain responsible for following up AEs that are serious, considered related to the study intervention or study procedures, or that caused the participant to discontinue the study intervention or study. See Appendix 4 for Definitions and Procedures for Recording, Evaluating, Follow-up, and Reporting AEs.

#### **4.5.1.1. Adverse Events of Special Interest**

Based on the known warnings and precautions identified in AIMOVIG (erenumab) prescribing information, summary tables will be created for the below adverse events of special interest reported by all participants regardless of frequency.

##### **4.5.1.1.1. *Injection Site Reactions***

This will include the subset of adverse events with a MedDRA coded HLT of *Injection Site Reaction*.

##### **4.5.1.1.2. *Constipation***

This will include the subset of adverse events with a MedDRA coded PT of *Constipation*.

##### **4.5.1.1.3. *Hypertension***

This will include the subset of adverse events with a MedDRA coded PT of *Hypertension*.

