9.4.5. Other safety Analyses

There will not be a formal statistical analysis for safety endpoints (adverse events, etc.); however, all adverse events will be summarized via tables and descriptive statistics as appropriate.

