#### **4.5.2. Additional Safety Assessments**

Additional adverse events grouped by MedDRA coded SOC (unless further specificity is listed below or required) with  $\geq 5\%$  occurrence in participants treated with erenumab-aooe will be supplemented with tables of the below evaluations.

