#### 4.5.2.5. Vital Signs

The following vital signs will be collected during the study:

- Blood pressure and pulse measurements.
- Blood pressure and pulse measurements should be preceded by at least 5 minutes of rest for the participant in a quiet setting without distractions (e.g., television, cell phones).
- Vital signs will be measured in a semi-supine position after 5 minutes rest and will include temperature, systolic and diastolic blood pressure, and pulse.
- AE tables will be supplemented if  $\geq 5\%$  of participants treated with erenumab-aooe experience potentially significant vital sign change AEs including those outlined below:
  - AEs that have a MedDRA coded PT of:
    - *Blood pressure systolic decreased*
    - *Blood pressure systolic increased*
    - *Blood pressure diastolic decreased*
    - *Blood pressure diastolic increased*
  - AEs that have a MedDRA coded PT of *Heart rate decreased* or *Heart rate increased*.
  - AEs that have a MedDRA coded PT of *Body temperature decreased* or *Body temperature increased*

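### The hypertension special-interest table rests on one preferred term and can miss blood-pressure elevations coded to terms the SAP itself treats as potentially significant

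*SAP*

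**What the plan says.** SAP 4.5.1.1 selects its special-interest events from the warnings and precautions in the product's prescribing information, and commits that "summary tables will be created for the below adverse events of special interest reported by all participants regardless of frequency". Three events follow. Injection site reactions are taken at the High Level Term (HLT). Constipation and hypertension are each taken as a single PT. For hypertension, SAP 4.5.1.1.3 reads "This will include the subset of adverse events with a MedDRA coded PT of" Hypertension, and nothing more.

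Raised blood pressure is dealt with again in SAP 4.5.2.5. There, AE tables are to be supplemented if at least 5% "of participants treated with erenumab-aooe experience potentially significant vital sign change AEs including those outlined below". The list under that sentence includes "Blood pressure systolic increased" and the matching diastolic term, together with the two pressure-decreased terms, heart rate and body temperature. The parent section, SAP 4.5.2, sets the general rule: other events with at least 5% "occurrence in participants treated with erenumab-aooe will be supplemented with tables of the below evaluations".

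Two wider statements also apply. SAP 4.5 says that "all safety endpoints will be summarized via tables and descriptive statistics as appropriate", and Protocol 9.4.5 says that "all adverse events will be summarized via tables and descriptive statistics as appropriate". Neither carries a frequency cut-off. SAP 4.5.1 plans final AE tables and leaves the MedDRA level to be chosen for each class of event.

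**The concern.** One risk is handled under two rules, and the coding of the event decides which applies. An elevation coded to Hypertension enters a table with no threshold. A clinically significant elevation coded to systolic or diastolic pressure increased does not enter that table at any frequency, and gets a supplementary table only at 5% or more. The SAP describes the second group as potentially significant, so by its own account these events are not trivial.

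The split is a realistic one. Vital signs are scheduled at all five visits and at early discontinuation. Protocol 10.3.1 and SAP 6.4.1 allow a vital-sign abnormality to be an AE when the investigator judges it clinically significant. A raised reading without a diagnosis of hypertension could be coded to one of the increased terms, and SAP 4.5.2.5 expects those terms to occur.

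Safety is a stated objective and no formal safety testing is planned, so the descriptive tables are the whole safety output. If the hypertension table is narrower than the risk it was set up to show, a reader may take a low count there as the study's evidence on blood pressure.

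**Working it through.** **Inputs.** Maximum treated: 54 (Protocol 1.1). Special-interest threshold: none (SAP 4.5.1.1). Supplement threshold: 5% of treated participants (SAP 4.5.2.5). Pressure-increased PTs named: two, systolic and diastolic (SAP 4.5.2.5). The documents give no event rate.

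**The plan's own figure.** The 54 is not in dispute, but it is the denominator. A two-sided paired *t*-test with d = 0.50, alpha 0.05 and target power 0.95, using the noncentral *t* distribution, gives n = 54 with power 0.9502. The stated size is reproduced.

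**Threshold as a count.** 0.05 × 54 = 2.7, so the supplement needs at least 3 participants. It also needs 3 at N = 50 (2.5) and N = 45 (2.25), and 2 at N = 40 (2.0).

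**Participants who could be in neither the special-interest table nor the supplement.** The SAP does not say whether the 5% applies to each PT or to the listed terms together. The introduction to 4.5.2 groups events by System Organ Class unless more specific terms are listed, and 4.5.2.5 lists PTs. The triggering sentence in 4.5.2.5, however, speaks of vital-sign change AEs as a group.

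| Reading of the 5% rule | Largest number in neither table | Share of 54 | Exact 95% CI |
|---|---|---|---|
| Pooled over listed terms | 3 − 1 = 2 | 3.7% | 0.5% to 12.7% |
| Per PT, different participants under each | 2 × (3 − 1) = 4 | 7.4% | 2.1% to 17.9% |
| Increased PTs moved into the special-interest group | 0 | 0% | – |

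These are ceilings on the number left to the general AE tables alone. Above the threshold a supplement appears, but under 4.5.1.1.3 as written the events still do not enter the hypertension table.

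**How often the supplement would be absent.** With X ~ Binomial(54, p), P(no supplement) = P(X ≤ 2), and P(cases exist but fall short) = P(X = 1) + P(X = 2). The rates p are assumed, and the threshold is applied to one blood-pressure-increased category alone.

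| Assumed p | P(X ≤ 2) | P(X = 1 or 2) | P(X ≥ 3) |
|---|---|---|---|
| 1% | 98% | 40% | 2% |
| 2% | 91% | 57% | 9% |
| 3% | 78% | 59% | 22% |
| 5% | 49% | 43% | 51% |

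If the rule pools pressure decreases, heart rate and temperature as well, the supplement would be triggered at least as often as the last column shows.

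**The case against.** The strongest reply is that nothing is hidden. A reader might infer that the pressure-increased events are shown only at 5% or more. The documents do not say that. The 5% rule governs supplementary tables. Protocol 9.4.5, SAP 4.5 and SAP 4.5.1 all promise AE summaries with no cut-off, so an event in one or two participants is still tabulated. This stands. What remains is that the MedDRA level of those tables is open, so the terms may be absorbed into a broader class, and nothing requires them to be counted with hypertension.

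A reader might also infer that measured blood pressure is never summarised. That goes too far. SAP 4.5 promises descriptive summaries as appropriate, and SAP 4.5.2 provides tables of the evaluations when the AE threshold is met. The supportable statement is that no specific, unconditional blood-pressure summary is defined.

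Nor can one say that the special-interest table will read low. Protocol 10.3.3 and SAP 6.4.3 ask for the diagnosis rather than individual signs whenever possible, which steers elevations towards Hypertension, and only abnormalities judged clinically significant become AEs. This narrows the split without closing it, because SAP 4.5.2.5 still lists the increased terms as expected codes.

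Two further extensions lack support. A reader might argue that a general pressure-increased term falls outside both lists. The documents name no such term, and the list in 4.5.2.5 is open-ended ("experience potentially significant vital sign change AEs including those outlined below"). A reader might also want the limits in exclusion criterion 16c used as on-treatment cut-offs. Those define uncontrolled hypertension for eligibility and require a confirmed reading; the documents give them no other role.

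Finally, the probabilities above rest on assumed rates and one reading of the threshold. They describe how often a supplement would be absent, not the size of any undercount.

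**Conclusion.** The point holds as a possible undercount in one descriptive table. The SAP promises a frequency-independent table for a labelled risk, populates it from one PT, and places two PTs it regards as potentially significant under a 5% condition. At 54 treated, up to 2 participants (pooled rule) or 4 participants (per-PT rule, no overlap) could appear only in the general AE tables. These ceilings need only the number treated and the SAP's wording. Whether any participant is affected depends on how elevations are recorded and coded, which the documents do not settle. No efficacy analysis is touched. The change is worth making because it is nearly free and makes the table match its purpose; SAP 4.5.1.1.1 already uses a broader grouping for injection site reactions.

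**What to change.** 1. In SAP 4.5.1.1.3, define the hypertension event of special interest as PT Hypertension plus PT Blood pressure systolic increased and PT Blood pressure diastolic increased, the two increased terms already named in 4.5.2.5. Tabulate the group at any frequency, counting each participant once, with the component PTs shown beneath.
2. In SAP 4.5.2.5, state whether the 5% condition applies to each PT or to the listed terms pooled.
3. Optionally, add to SAP 4.5.2.5 an unconditional descriptive summary of systolic and diastolic pressure by visit, with change from Visit 2. In a single-arm study this describes the data and does not estimate a drug effect.

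The cost is a few lines of SAP text and one or two tables from data already collected and coded. Treatment, visits and sample size are unchanged.
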